## LIST OF ABBREVIATIONS AND DEFINITIONS OF TERMS

ADT	Androgen deprivation therapy
AE	Adverse event
AR	Androgen receptor
C-11	Carbon-11
CDR	Correct detection rate
CFR	Code of Federal Regulations
CLR	Correct localization rate
ClCr	Creatinine clearance
CRF	Case report form
CT	Computed tomography
CTCAE	Common Terminology Criteria for Adverse Events
Cu-64	Copper-64
CV	Curriculum Vitae
ECG	Electrocardiogram
EDC	Electronic data capture
eCRF	Electronic case report form
F-18	Fluorine-18
FDA	Food and Drug Administration
Ga-68	Gallium-68
GCP	Good Clinical Practice
I&T	Imaging and Therapeutic
ICF	Informed consent form
ICH	International Conference on Harmonisation
ICL	Imaging Core Laboratory
ID	Injected dose
IEC	Independent Ethics Committee
IRB	Institutional Review Board
IME	Imaging evaluable
ITE	Intent to evaluate
LNM	Lymph node metastases
MBq	Megabecquerel
mCi	Millicurie
mCRPC	Metastatic castrate-resistant prostate cancer
MedDRA	Medical Dictionary for Regulatory Activities
MIRD	Committee on Medical Internal Radiation Dose
MRI	Magnetic Resonance Imaging
NCI	National Cancer Institute
PC	Prostate cancer
PET	Positron Emission Tomography
PSA	Prostate Specific Antigen
PSMA	Prostate Specific Membrane Antigen
ROI	Regions of interest
SAE	Serious adverse event
SAP	Statistical Analysis Plan

CURCu64PSM0001

Version 5.0 16Feb2022

SOP	Standard Operating Procedure
SUV max	Maximum standard uptake value
UP	Unanticipated problem
US	United States
VOI	Volume of interest
WHO	World Health Organization

## PROTOCOL SYNOPSIS

Title of Study	A Multi-Center, Open-Label, Randomized Phase 1/2 Study of Copper Cu 64 PSMA I&T Injection in Patients with Histologically Proven Metastatic Prostate Cancer
Phase of Clinical Trial	Phase 1/2
Indication	Detection and localization of recurrent prostate cancer in men with biochemical recurrence based on elevated blood prostate specific antigen (PSA) levels following prior treatment.
Number of Sites	5-10
Drug Product	Copper Cu 64 PSMA I&T
Study Objectives	
Phase 1
 
Primary Objectives:
 
The primary objectives of the Phase 1 portion of this study are:
 

1. To assess the safety and determine radiation dosimetry estimates following intravenous administration of 5, 7, and 9 mCi doses of copper Cu 64 PSMA I&T injection in patients with recurrent prostate cancer. Safety will be assessed by monitoring adverse events, clinical chemistry, hematology, urinalysis, vital signs, ECG, and determination of radiation absorbed dose estimates.

2. To assess the PET/CT image quality following intravenous administration of 5, 7, and 9 mCi doses of copper Cu 64 PSMA I&T injection to determine an acceptable dose for obtaining diagnostic quality PET/CT images.

 
Phase 2
 
Primary Objectives:
 
The primary objectives of the Phase 2 portion of this study are:
 

1. To determine the region-level correct localization rate (CLR) of copper Cu 64 PSMA I&T injection PET/CT imaging for the detection of recurrent metastatic prostate cancer at 1 hour and 4 hours post injection. The CLR is defined as the percentage of regions containing at least one true PET positive lesion, with exactly localized correspondence between PET/CT imaging and the Composite Reference Standard regardless of any co-existent false positive findings, within the same region, out of all regions containing at least one PET positive finding.

	
2. To determine the patient-level correct detection rate (CDR) of copper Cu 64 PSMA I&T injection PET/CT imaging for the detection of recurrent metastatic prostate cancer at 1 hour and 4 hours post injection. The CDR is defined as the percentage of patients who have at least one true PET positive lesion, with exactly localized correspondence between PET imaging and the Composite Reference Standard, regardless of any co-existent false positive findings, out of all patients who are scanned.
 
3. To assess the safety of copper Cu 64 PSMA I&T injection in patients with recurrent prostate cancer. Safety will be assessed by monitoring adverse events, clinical chemistry, hematology, urinalysis, ECG, and vital signs.
 
Secondary Objective:
 
1. To compare the diagnostic quality of PET/CT images obtained at 1 hour and 4 hours post copper Cu 64 PSMA I&T injection.

Study Design	
This is a prospective, open-label Phase 1/2 study to evaluate copper Cu 64 PSMA I&T injection for PET/CT imaging in patients with recurrent metastatic prostate cancer after radical prostatectomy or radiation therapy.
 
Phase 1
 
The Phase 1 portion of the study will include a total of 12 patients with metastatic prostate cancer. Patients will be randomized into three groups of four patients. Patients in each group will receive a single intravenous dose of 5, 7, or 9 mCi of copper Cu 64 PSMA I&T. Whole-body PET/CT images will be acquired at 1 hour <math>\pm</math> 15 minutes, 4 hours <math>\pm</math> 0.5 hours, and 24 hours <math>\pm</math> 2.0 hours post-injection to determine radiation absorbed dose estimates.
 
The 1 hour and 4-hour PET/CT images will be evaluated independently by three readers blinded to all patient information and dose administered to assess the quality of the images (24 PET/CT image sets total). The assessments will be used to determine an acceptable dose to be administered for the Phase 2 study.
 
Phase 2
 
The Phase 2 portion of the study will include a separate group of 26 patients with metastatic prostate cancer. Each patient will be administered the same intravenous dose of copper Cu 64 PSMA I&T injection determined in the Phase 1 study. PET/CT images will be acquired for all patients at 1 hour <math>\pm</math> 15 minutes and 4 hours <math>\pm</math> 30 minutes post copper Cu 64 PSMA I&T injection.
 
The PET/CT images will be interpreted independently by three readers blinded to all patient information. Each patient study will be assessed and scored for the detection of prostate cancer. Specifically, each reader will categorize images as "Disease" or "No Disease" based only on tumor

	
uptake of copper Cu 64 PSMA-I&T in each of the four regions: 1) prostate bed or prostate gland, 2) lymph nodes (pelvic and extra pelvic), 3) bone, and 4) viscera/soft tissue. Analysis of the reads will be used for determination of the CLR and CDR for 1 hour and 4-hour post-injection imaging of copper Cu 64 PSMA I&T PET/CT by comparison to the Composite Reference Standard.

Study Population	
The study will include patients with metastatic proven prostate adenocarcinoma.
 
Phase 1: Total of 12 patients.
 
Inclusion Criteria:
 

1. Patients with histologically proven prostate adenocarcinoma.

2. Prior radical prostatectomy or radiation therapy with curative intent.

3. Recurrence of disease, defined as:

a. Prior Radical Prostatectomy: PSA > 0.2 ng/mL, or

b. Prior Radiation Therapy: 2 ng/mL rise in PSA over post-treatment nadir.

4. Patients with at least one extraprostatic site of disease suspected based on prior imaging or diagnosed by biopsy.

5. Age greater than or equal to 18 years.

6. Able to understand and provide signed written informed consent.

 
Exclusion Criteria:
 

1. Body weight greater than 350 lb. (158 kg).

2. Investigational therapy within the past 30 days.

3. Creatinine clearance (ClCr) less than 30 mL/min.

4. Participants who are capable of fathering a child and who are unwilling to take precautions to prevent pregnancy.

 
Phase 2: Total of 26 patients.
 
Inclusion Criteria:
 

1. Patients with histologically proven prostate adenocarcinoma.

2. Prior radical prostatectomy or radiation therapy with curative intent.

3. Recurrence of disease defined as:

a. Prior Radical Prostatectomy: PSA > 0.2 ng/mL, or

	
b. Prior Radiation Therapy: 2 ng/mL rise in PSA over post-treatment nadir
 
4. Patients with at least one extraprostatic site of disease suspected based on prior imaging or diagnosed by biopsy.
 
5. Age greater than or equal to 18 years.
 
6. Able to understand and provide signed written informed consent.
 
Exclusion Criteria:
 

1. Androgen deprivation therapy (ADT) or other therapies targeting the androgen pathway unless subject has a rising PSA level.

2. Body weight greater than 350 lb (158 kg).

3. Investigational therapy within the past 30 days.

4. Creatinine clearance (ClCr) less than 30 mL/min.

5. Participants who are capable of fathering a child and who are unwilling to take precautions to prevent pregnancy.

Phase 1 Study Procedures	
A total of 12 patients will be randomly assigned to one of three groups, four patients per group, to receive a single intravenous injection of 5, 7, or 9 mCi of copper Cu 64 PSMA I&T.
 
Screening:
 
All patients will be screened to ensure they meet all inclusion and no exclusion criteria for enrollment in the study. Written informed consent will be obtained for all patients enrolled in the study.
 
Baseline Assessments:
 
Routine clinical chemistry, hematology, and urinalysis will be obtained for all patients prior to dosing. PSA will also be obtained for all patients prior to dosing.
 
Medical history and physical examination will be performed prior to dosing. This will include information on the history of the prostate cancer. Concomitant medication history will also be obtained.
 
A baseline 12-lead ECG will be obtained prior to dosing. Vital signs including heart rate, respiratory rate, and blood pressure will be assessed prior to dosing.
 
Randomization:
 
Patients will be randomized to receive a single dose of 5, 7 or 9 mCi of copper Cu 64 PSMA I&T injection.

	
Pharmacokinetic/Radiation Absorbed Dose:
 
Whole body PET/CT scans will be acquired at 1 hour <math>\pm</math> 15 minutes, 4 hours <math>\pm</math> 30 minutes, and 24 hours <math>\pm</math> 2.0 hours post-injection. CT scans will be acquired for attenuation correction and anatomical reference. Images will be acquired using calibrated time-of-flight mode using digital scanners. For calculation of radiation absorbed dose estimates, volumes of interest (VOI) will be delineated for the kidneys, liver, lungs, spleen, urinary bladder, salivary glands, and total body. Image count values will be corrected for radioactive decay, scanner response, start/stop times, and net injected dose. The remaining activity will be assumed to be distributed homogeneously throughout the body after adjusting for activity in the organs, blood, and voided urine. Organ-specific and whole-body radiation dose analysis will be performed using OLINDA/EXM software, following Medical Internal Radiation Dose (MIRD) guidelines.
 
Voided urine activity values will be accounted for in the dosimetry analysis by collection of all urine for 0-1 hour and 1-4 hour intervals post-injection. The total voided urine volume for each interval will be measured and the total radioactivity calculated by comparison to a calibrated standardized sample or per Site's standard methods. Calibrated urine voiding curves will be determined and included in the dosimetry analysis.
 
Venous blood samples will be collected prior to copper Cu 64 PSMA I&T injection and at 1 hour, 2 hours, 4 hours and 24 hours post-injection. The radioactivity concentration in the blood samples will be determined on a per-milliliter basis using a calibrated standard measured in a well counter for dosimetry analysis or per Site's standard methods. No metabolite analysis will be performed on the blood or urine samples.
 
Estimates of radiation absorbed dose will be calculated for all patients with the data from the VOI analysis at each imaging timepoint.
 
Dose-Range Evaluation:
 
The 1 hour and 4-hour post-injection PET/CT images for all patients will be evaluated for diagnostic image quality by three independent readers blinded to all patient information and doses administered. Image quality will be assessed using the following scoring system: 0 = inadequate (grainy images with poor delineation of lesions); 1 = questionable (clear images, but lesion delineation is suboptimal and small lesions [1 cm] are hard to assess); 2 = acceptable (clear images, large and small lesion delineation is possible). Cohort scores will be calculated by adding the average patient image scores in each dosing group.
 
In addition, the blinded readers will record lesion signal-to-noise, Maximum Standard Uptake Value (SUVmax), lesion-contrast-to-noise and lesion-to-normal tissue values derived from VOI values as described in the Independent Reader Manual. The cohort scores and image quality

--	---

	
evaluations will be used in the determination of the injected dose value for the Phase 2 study.
 
Safety Assessments:
 
All patients will be followed for adverse events for 24 hours post-injection. Severity of adverse events will be assessed independently by the Investigators and graded using the National Cancer Institute Common Terminology Criteria for Adverse Events version 5.0, in which Grades 1, 2, 3, 4, and 5 describe adverse events as mild, moderate, severe, or medically significant but not life-threatening, life-threatening, and death related to adverse event, respectively.
 
Routine clinical chemistry, hematology, PSA, and urinalysis will be performed at 4 hours post-injection on all patients. If no clinically significant changes are noted, no additional follow-up will be performed. If significant findings are noted, they will be reassessed at 24 hours post-injection and followed until values return to normal or baseline, or until the Investigator and Medical Monitor determine it is no longer necessary.
 
A 12-lead ECG will be obtained at 30 minutes and 3.5 hours post-injection for all patients. If no clinically significant changes are noted, no additional follow-up will be performed. If significant findings are noted, the patient will be reassessed at 24 hours post-injection and followed until values return to normal or baseline, or until the Investigator and Medical Monitor determine it is no longer necessary.
 
Vital signs including heart rate, blood pressure, and respiratory rate will be obtained at 5 minutes, 30 minutes, 1 hour and 4 hours post-injection on all patients. If no clinically significant changes are noted, no additional follow-up will be performed. If significant findings are noted, they will be reassessed at 24 hours post-injection.
 
Follow-up:
 
Patients will be seen 24 hours post-injection for assessment of adverse events, clinically significant lab or ECG values or clinically significant vital signs. Patients with clinically significant changes will be followed until such events resolve or as decided by the Investigator and Medical Monitor.

--	--

Phase 2 Study Procedures	
A total of 26 patients will be included in the Phase 2 portion of the study.
 
Screening:
 
All patients will be screened to ensure they meet all inclusion and no exclusion criteria for enrollment in the study. Written informed consent will be obtained for all patients enrolled in the study.

---------------------------------	---

	
Baseline Assessments:
 
Routine clinical chemistry, hematology, and urinalysis will be obtained for all patients prior to dosing. PSA will also be obtained for all patients prior to dosing.
 
Medical history and physical examination will be performed prior to dosing. This will include information on the history of the prostate cancer. Concomitant medication history will also be obtained.
 
Imaging Procedure:
 
All patients will undergo PET/CT imaging at 1 hour <math>\pm</math> 15 minutes and 4 hours <math>\pm</math> 30 minutes following copper Cu 64 PSMA I&T injection using the dose determined in Phase 1. The 1 hour and 4-hour images will be independently read by three experienced blinded readers for the detection of prostate cancer. Specifically, each reader will categorize images as “Disease” or “No Disease” based only on tumor uptake of copper Cu 64 PSMA-I&T in each of the four regions: 1) prostate bed or prostate gland, 2) lymph nodes (pelvic and extra pelvic), 3) bone, and 4) viscera/soft tissue.
 
Efficacy Analysis:
 
Composite Reference Standard
 
All patients will undergo an efficacy assessment based on copper Cu 64 PSMA I&T PET/CT results and the results of clinical presentation for evaluation against the Composite Reference Standard.
 
The Composite Reference Standard is defined as follows:
 

1. Local histopathology obtained from prostate cancer surgery or biopsy obtained within 60 days before or following copper Cu 64 PSMA I&T PET/CT, or

2. If histopathology is not available, anatomical correlation of conventional image findings (e.g., targeted MRI or CT or any FDA-approved PET PSMA agent) that are acquired prior to locoregional or systemic treatment and within 60 days before or following copper Cu 64 PSMA I&T PET/CT

 
Safety Assessments:
 
All patients will be followed for adverse events for 24 hours post-injection. Severity of adverse events will be assessed independently by the Investigators and graded using the National Cancer Institute Common Terminology Criteria for Adverse Events version 5.0, in which Grades 1, 2, 3, 4, and 5 describe adverse events as mild, moderate, severe or medically significant but not life-threatening, life-threatening, and death related to the adverse event, respectively.

--	---

	
Routine clinical chemistry, hematology, PSA, and urinalysis will be performed at 4 hours post-injection on all patients. If no clinically significant changes are noted, no additional follow-up will be performed. If significant findings are noted, they will be reassessed at 24 hours post-injection and followed until values return to normal or baseline, or until the Investigator and Medical Monitor determine it is no longer necessary.
 
A 12-lead ECG will be obtained at 30 minutes and 3.5 hours post-injection for all patients. If no clinically significant changes are noted, no additional follow-up will be performed. If significant findings are noted, the patient will be reassessed at 24 hours post-injection and followed until values return to normal or baseline, or until the Investigator and Medical Monitor determine it is no longer necessary.
 
Vital signs including heart rate, blood pressure, and respiratory rate will be obtained at 5 minutes, 30 minutes, 1-hour and 4-hour post-injection on all patients. If no clinically significant changes are noted, no additional follow-up will be performed. If significant findings are noted, they will be reassessed at 24 hours post-injection.
 
Follow-up:
 
Patients will be contacted 24 hours post-injection for assessment of adverse events, clinically significant lab or ECG values or clinically significant vital signs. Patients with clinically significant changes will be followed until such events resolve or as decided by the Investigator and Medical Monitor.
 
Patients will continue to be followed for disease progression by their physician per their standard of care. Any conventional imaging (dedicated CT, MRI, bone scan, or FDA-approved PET/CT) based on the site's clinical Standard of Care (SOC) performed within 12 months of administration may be collected to evaluate disease progression.

Statistical Analysis	
Sample Size:
 
Phase 1:
 
The sample size for the Phase 1 portion of the study is not powered for hypothesis testing but is an appropriate sample size for calculation of the radiation absorbed dose following administration of copper Cu 64 PSMA I&T injection. In addition, four patients per dose level is an adequate sample to determine the lowest dose level yielding diagnostic quality images at 1- and 4-hours post-injection. This is defined as a three-point assessment of image quality.
 
Study Endpoints:
 
Phase 2:
 
Primary Efficacy Endpoints:

	
1. To determine the region-level correct localization rate (CLR) of copper Cu 64 PSMA I&T injection PET/CT imaging for the detection of recurrent metastatic prostate cancer at 1- and 4-hours post-injection. The CLR is defined as the percentage of regions containing at least one true PET positive lesion, with exactly localized correspondence between PET/CT imaging and the Composite Reference Standard regardless of any co-existent false positive findings, within the same region, out of all regions containing at least one PET positive finding.
 
2. To determine the patient-level correct detection rate (CDR) of copper Cu 64 PSMA I&T injection PET/CT imaging for the detection of recurrent metastatic prostate cancer at 1 hour and 4 hours post-injection. The CDR is defined as the percentage of patients who have a least one true PET positive lesion with exactly localized correspondence between PET imaging and the Composite Reference Standard regardless of any co-existent false positive findings, out of all patients who are scanned
 
Since all patients enrolled in the study will have disease, the CLR is a measure of the sensitivity of the copper Cu 64 PSMA I&T injection scan. Current methods have a CLR of 60%; thus, the hypothesis to be tested in the Phase 2 portion of the study is: H0: <math>\pi_C = \pi_0</math> versus HA: <math>\pi_C > \pi_0</math> where <math>\pi_C</math> is the CLR for copper Cu 64 PSMA I&T injection and <math>\pi_0</math> is the CLR from the literature (estimated to be 60%).
 
This hypothesis will be tested using an exact one-sample binomial test with a one-sided <math>\alpha=0.025</math>.
 
Secondary Objective:
 
The secondary objective for the Phase 2 study is to compare the diagnostic quality of PET/CT images obtained at 1 hour and 4 hours post copper Cu 64 PSMA I&T injection.
 
Safety Endpoint:
 
To assess the safety of copper Cu 64 PSMA I&T injection in patients with recurrent prostate cancer. Safety will be assessed by monitoring adverse events, clinical chemistry, hematology, urinalysis, ECG, and vital signs.
 
Analysis Populations:
 
Several analysis populations of patients are defined, which may provide a more complete description of the collected data, provide a logical mechanism for grouping and listing results based on an applied analysis, and/or allow appropriate stratification of various analyses.
 
1. The Enrolled Patient Population (EPP) represents patients who sign an Informed Consent Form and have baseline data.

--	---

	
2. The Intent-to-Evaluate (ITE) Population are patients in the Enrolled Patient Population who satisfy the eligibility criteria and who have undergone a copper Cu 64 PSMA I&T imaging study.
 
3. The Imaging Evaluable (IME) Population are patients in the ITE Population who have completed imaging procedures according to the protocol with technically satisfactory results.
 
4. The Safety Population are patients who are administered copper Cu 64 PSMA I&T injection.

--	--

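### The Phase 1 cohort image-quality score is a sum over patients, so it can distort the comparison between dose groups if they end up with unequal numbers of evaluable patients

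*Combined protocol and SAP*

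**What the plan says.** All references are to the Protocol Synopsis.

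- **Group size** (Phase 1 Study Procedures): "A total of 12 patients will be randomly assigned to one of three groups, four patients per group".
- **Scale and reading** (Dose-Range Evaluation): the 1 h and 4 h images are "evaluated for diagnostic image quality by three independent readers blinded to all patient information and doses administered". Each image is scored 0 (inadequate), 1 (questionable) or 2, the top category being "2 = acceptable (clear images, large and small lesion delineation is possible").
- **Cohort score** (Dose-Range Evaluation): "Cohort scores will be calculated by adding the average patient image scores in each dosing group". No division by group size is given. The sentence does not say whether a patient's average is taken over readers, timepoints or both.
- **Use** (end of Dose-Range Evaluation): the cohort scores and image quality "evaluations will be used in the determination of the injected dose value for the Phase 2 study". The readers also record lesion signal-to-noise, SUVmax, contrast-to-noise and lesion-to-normal tissue values.
- **Aim** (Statistical Analysis, Sample Size): "four patients per dose level is an adequate sample to determine the lowest dose level yielding diagnostic quality images". No cohort-score threshold is given.
- **Incomplete imaging** (Analysis Populations): the Imaging Evaluable Population consists of patients who "have completed imaging procedures according to the protocol with technically satisfactory results". This is not linked to the cohort score. The synopsis gives no Phase 1 replacement rule and no rule for a missing or unread scan.

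**The concern.** A score that informs a choice between dose groups should mean the same thing in every group. A sum of patient averages does so only while every group has the same number of contributors. Once one group has three and another four, the sum mixes how good the images were with how many patients supplied them. The same applies if a group is judged against a standard and not against the other groups: a fixed total is harder to reach with three patients than with four.

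At stake is one named input to the Phase 2 injected dose. The Imaging Evaluable definition shows that the plan foresees some unsatisfactory imaging. With four patients per group, the loss of one is a quarter of the group.

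**Working it through.** **Inputs from the synopsis.** Three groups of four patients, two scored timepoints, three readers, image scores of 0, 1 or 2.

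**Plan's own count.** 3 × 4 = 12 patients, and 12 × 2 = 24, which agrees with the "24 PET/CT image sets total" in Study Design. The plan states no numerical cohort score to reproduce.

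**Formula.** Let n be the number of contributing patients and m the mean of their average scores (0 to 2). Cohort score S = n × m.

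**Ceiling.** n = 4: 4 × 2 = 8. n = 3: 3 × 2 = 6. The ceiling drops by 2/8 = 25%.

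**Break-even.** A three-patient group with mean m3 ties a full group with mean m4 when 3 × m3 = 4 × m4, that is, when m4 = 0.75 × m3.

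| Three-patient mean | Sum | Full-group mean that ties |
|---|---|---|
| 2.00 | 6.0 | 1.50 |
| 1.67 | 5.0 | 1.25 |
| 1.50 | 4.5 | 1.125 |
| 1.00 | 3.0 | 0.75 |

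The order by sum contradicts the order by mean when m4 lies strictly between 0.75 × m3 and m3. Example: m3 = 2.00 gives 6.0, and m4 = 5/3 = 1.67 gives 4 × 5/3 = 6.67. The reduced group has the better images and the lower score. A mean of 5/3 is attainable with integer scores from three readers.

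**How often sizes would differ (assumption).** The documents give no loss rate. If each patient independently has probability q of not contributing, with no replacement, then P(sizes not all equal) = 1 − Σk [C(4,k)(1−q)^k q^(4−k)]³. This gives 0.305 for q = 0.03, 0.455 for q = 0.05 and 0.693 for q = 0.10. These are probabilities of unequal sizes only.

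**How often the order would be affected, given a loss (assumption).** Two groups, A and B, of identical underlying quality were simulated 100,000 times for each score distribution, with one independent score per patient.

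| Assumed P(0)/P(1)/P(2) | A below B, 4 vs 4 | A below B, 3 vs 4 | A has higher mean but lower sum, 3 vs 4 |
|---|---|---|---|
| 0.1/0.3/0.6 | 0.39 | 0.72 | 0.20 |
| 0.05/0.15/0.8 | 0.35 | 0.82 | 0.22 |
| 0.2/0.4/0.4 | 0.41 | 0.64 | 0.12 |

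**After the change.** Dividing by n keeps the scale at 0 to 2 for any group size. In the example the groups score 2.00 and 1.67, in the order of their image quality.

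**The case against.** The strongest case against has five parts.

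1. **The design fixes four per group and counts all 24 image sets.** At 4/4/4 the sum and the mean order the groups identically. This stands: the problem is conditional on unequal groups. Only the synopsis was available, and it refers to an Independent Reader Manual, so a replacement or missing-scan rule elsewhere cannot be excluded.
2. **One failed scan need not remove a patient.** A reader might infer that any single failed or unread scan changes the order of the groups. The text does not support that. If a patient's average runs over readers and timepoints, one lost scan or read leaves an average and the group keeps four terms. The patient drops out only if nothing is left to average, or if scores are kept by timepoint, which the text does not say. Losing a whole patient lowers the sum unless that patient would have averaged 0, but it reverses the order only within the range shown above.
3. **Poor images are not missing images.** Grainy images with poor lesion delineation score 0 and remain in the sum. This stands: only images not acquired or not read create the artefact.
4. **There is no ranking rule.** The stated aim is the lowest dose level with diagnostic-quality images, not the highest total, and other image metrics enter the decision. With 12 patients, a group of three would be obvious to whoever compares the scores. This stands, and it limits the consequence.
5. **The sentence can be read differently.** Adding a group's 1 h average to its 4 h average would not depend on group size. This is the less natural reading, but that it is available is a further reason to make the sentence explicit.

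**Conclusion.** The point holds in a limited, conditional form. On its natural reading the Phase 1 cohort score depends on the number of contributing patients: its ceiling falls from 8 to 6 when one of four is lost, and a three-patient group needs 4/3 of the full group's mean just to tie. If groups become unequal, the comparison between them can be distorted.

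Two stronger inferences are not supported. The probabilities of 31% to 69% for unequal group sizes rest on assumed loss rates without replacement, and they are not probabilities of a reversed comparison or a wrong dose. The simulated reversal rates of about 12% to 22% apply only once a patient has been lost, and they rest on assumed score distributions. Because no ranking rule is stated and other metrics contribute, a changed dose decision is possible but not shown. This is a minor, inexpensive clarification in a phase that is not powered for hypothesis testing.

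**What to change.** In the Dose-Range Evaluation text:

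- Define the cohort score as the mean, not the sum, of patient average scores over evaluable patients, separately for 1 h and 4 h, and state that each patient's average at a timepoint is taken over the readers.
- Report for each group and timepoint the number evaluable and the number of patients at each score level.
- State that a scan acquired and read as inadequate is scored 0, while a scan not acquired or not read is missing.

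The cost is a few sentences and one small table, with no new data. The one downside is that a mean can hide lost scans, which is why the number evaluable should stand beside it. With four evaluable patients in every group, the order at each timepoint is the same as under the sum. No dose or threshold is proposed.

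### The Phase 2 read as described gives a Disease / No Disease call in four broad regions, which does not supply the lesion locations that the CLR and CDR definitions require

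*Combined protocol and SAP*

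**What the plan says.** **The read.** Protocol Synopsis, Study Design (Phase 2) and Phase 2 Study Procedures (Imaging Procedure): three blinded readers each make a Disease / No Disease call "in each of the four regions: 1) prostate bed or prostate gland, 2) lymph nodes (pelvic and extra pelvic"), 3) bone and 4) viscera/soft tissue. All nodes form one region, and so does all bone.

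**Its use.** Study Design (Phase 2): "Analysis of the reads will be used for determination of the CLR and CDR for 1 hour and 4-hour post-injection imaging", by comparison with the Composite Reference Standard.

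**The endpoints.** Study Objectives and Statistical Analysis (Primary Efficacy Endpoints):
- CLR counts regions with at least one true PET-positive lesion "with exactly localized correspondence between PET/CT imaging and the Composite Reference Standard regardless of any co-existent false positive findings, within the same region". Its denominator is "out of all regions containing at least one PET positive finding".
- CDR counts patients with at least one true PET-positive lesion "with exactly localized correspondence between PET imaging and the Composite Reference Standard regardless of any co-existent false positive findings". Its denominator is all scanned patients.

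**The test.** CLR is tested against 60% with an exact one-sample binomial test at one-sided 0.025. No test is stated for CDR.

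**The reference.** Phase 2 Study Procedures (Composite Reference Standard): local histopathology or, failing that, anatomical correlation of conventional imaging findings or an approved PSMA PET. The text does not say how reference lesions are recorded or matched to PET lesions.

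**The concern.** The region is the counting unit for CLR, but success is decided by a lesion match inside the region. CDR uses the same lesion criterion at patient level. The allowance for co-existing false positives confirms this reading: it forgives extra findings only once a true, exactly located lesion is present.

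A yes/no call for a whole region carries no location. Suppose PET shows a pelvic node and the reference shows only a retroperitoneal node. Under the definition this nodal region is a failure. From the reader's call alone it cannot be told apart from a success.

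Both primary efficacy endpoints depend on this step, and so does the only stated hypothesis test. If location is not captured at the time of the read, supplying it later would mean reading the scans again.

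**Working it through.** **1. What the definitions need and what the read gives**

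| Needed for CLR and CDR | In the Phase 2 text supplied |
|---|---|
| Location of each PET-positive lesion | Disease / No Disease per region |
| Location of each reference lesion | Sources of the reference standard, but no recording format |
| Meaning of exact localization | Not defined |
| Who matches lesions, and by what rule | Not stated |

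Lesion-level values (signal-to-noise, SUVmax, contrast) and the Independent Reader Manual are mentioned only under the Phase 1 Dose-Range Evaluation.

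**2. Direction if region agreement were scored instead**

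Every exact lesion match is also a region agreement, but the reverse does not hold. The numerators can therefore only stay the same or grow. The denominators (PET-positive regions for CLR, scanned patients for CDR) do not change. Hence CLR and CDR by region agreement are equal to or above CLR and CDR as defined.

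**3. Illustration of size for CLR**

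The plan states no Phase 2 power, alternative CLR or expected number of positive regions, so there is no figure of its own to reproduce.

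*From the documents:* null 0.60; exact binomial; one-sided 0.025.

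*Assumed, not in the documents:* 26 independent PET-positive regions (one per patient); true exact-match CLR of 0.60; a share a of positive regions that are nodal, 0.40 to 0.50; and a share d of those nodal regions that are positive on both sides but at different nodes, 0.10 to 0.30.

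Rejection rule: the smallest r with P(X ≥ r | 26, 0.60) ≤ 0.025.
- P(X ≥ 20) = 0.0559, too large.
- P(X ≥ 21) = 0.0214. So reject at 21 of 26 (80.8%), with actual size 2.1%.

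Apparent CLR = 0.60 + a × d.
- Low: 0.60 + 0.40 × 0.10 = 0.64
- High: 0.60 + 0.50 × 0.30 = 0.75

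| Apparent CLR | P(X ≥ 21 of 26) |
|---|---|
| 0.60 | 0.021 |
| 0.64 | 0.053 |
| 0.68 | 0.115 |
| 0.70 | 0.163 |
| 0.72 | 0.223 |
| 0.75 | 0.337 |

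**4. How demanding the assumptions are**

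If nodal regions also have a true CLR of 0.60, then 40% of positive nodal regions have no exact match. The low end then means that 0.10/0.40 = 25% of those non-matching regions contain a different reference-positive node; the high end means 0.30/0.40 = 75%. The upper figures therefore need a high rate of discordance.

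**5. Sensitivity**

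Let f be the share of all non-matching PET-positive regions that still agree at region level. Then apparent CLR = 0.60 + 0.40 × f. With 26 regions:
- f = 0.05: CLR 0.62, false rejection 0.034
- f = 0.25: CLR 0.70, false rejection 0.163
- f = 0.50: CLR 0.80, false rejection 0.578

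With 52 regions (two per patient, also assumed), rejection needs 39 of 52 and the size is 0.0173. False rejection is then 0.063 at f = 0.10 and 0.267 at f = 0.25.

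All these figures treat regions as independent. Regions within one patient are clustered, so they are approximate on that account too.

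**The case against.** The strongest reply has four parts.

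- **The endpoint text is already right.** CLR and CDR as written demand exact correspondence, so the pelvic/retroperitoneal example fails the definition. Inflation needs an analyst who departs from that definition. This stands: the plan omits a step; it does not prescribe a wrong one. The reference standard is nowhere said to be scored as a yes/no per region, and anatomical correlation is site-based language.
- **The supplied text is a synopsis.** A reader manual or case report form may capture location. The abbreviation list includes an imaging core laboratory and regions of interest that the supplied text does not go on to use, and a reader manual exists. This stands as a limit on the claim: one mention of the manual, in Phase 1, does not show that it omits Phase 2 lesion location.
- **The size rests on unsourced inputs.** This stands. The binomial tails reproduce, but the number of regions, the nodal share and the discordance rate are assumptions.
- **The 60% null concerns CLR only.** This stands.

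A reader might infer that lesion location is not recorded at all, that the endpoints cannot be computed, or that they would be inflated. The documents support none of these. In "based only on tumor uptake of copper Cu 64", the word limiting the call refers to its basis, not to the data captured. Location data from another form would make the endpoints computable, and the bias is conditional and could be zero.

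What the reply does not remove is the mismatch: the reads described are named as the source of both endpoints, and they lack the information that both endpoints require.

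**Conclusion.** The point holds in conditional form. From the Phase 2 read as described, exact lesion correspondence cannot be established, and no other Phase 2 text supplied provides the location data or a matching rule. Scoring by region agreement would move CLR and CDR upward or leave them unchanged, and for CLR this favours rejecting 60%.

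The size is unknown. The range of 5% to 34% false rejection, against 2.1% with exact matching, is an illustration that depends on the assumed 26 independent positive regions, a true CLR of 60% and an apparent CLR of 64% to 75%. The change should be made because it alters what is collected for both primary efficacy endpoints, is cheap before the reads, and is hard to recover afterwards.

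**What to change.** For each region called Disease:

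1. Have each reader record the location of every PET-positive lesion, or at least of those to be matched, finely enough to identify the individual lesion: nodal station and side, bone and level or part, organ and segment, or image coordinates. A bone or organ name alone is too coarse, since two different lesions could still agree.
2. Record reference-standard lesions in the same way.
3. Define exact localization as a match on that recorded location.
4. State who applies the match, blinded to outcome.
5. Count a region (CLR) or patient (CDR) as correct only when at least one such match exists.

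If existing forms or the reader manual already do this for Phase 2, a sentence in the protocol that says so and gives the rule is enough.

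**Cost:** a few more fields on the reader and reference-standard forms and slightly longer reads. No extra readers, scans or patients.
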